7. SUBJECT RESTRICTIONS

7.1. Prior and Concomitant Medications

All prescription and over-the-counter medications, dietary supplements (including vitamins), and herbal supplements taken by the subject within 30 days (6 months for antidepressant therapy) before Day 1 (Visit 2) will be recorded on the Prior and Concomitant Medications page of the eCRF.

No antidepressant medication or dose changes are permitted from Day 1 through Day 57 (or ET visit) unless approved by the Study Medical Monitor (or designee).

The following medications listed in Table 2 are prohibited for all subjects beginning 30 days before Day 1 (Visit 2) until the end of the Study Treatment Period (Day 57 or ET visit). If a subject is prescribed treatment with a prohibited medication during the conduct of the study, the investigator should contact the Sponsor or designee to review the relevant clinical information and medication treatment to determine subject disposition.

Table 2: Prohibited Concomitant Medications

Prohibited Concomitant Medication

Glutamate modulators, eg, esketamine or ketamine, memantine, riluzole

Salvinorin A (Sal A) or salvia divinorum (street names include Maria Pastora, Sally-D, and Salvia)

Other antidepressant medications including tricyclic (eg, clomipramine) or tetracyclic (eg, maprotiline) antidepressants (TCAs), monoamine oxidase inhibitors (MAOIs)

Antipsychotics, including injectable/depot antipsychotics (lifetime)

Stimulants (eg, amphetamines, dextroamphetamine, methylphenidate, methamphetamine, modafinil, armodafinil)

Kappa opioid antagonists (eg, buprenorphine)

Dopamine agonists such as pramipexole

Strong and moderate CYP3A4 inhibitors, including but not limited to, clarithromycin, itraconazole, ketoconazole^a, nefazodone, saquinavir, suboxone, and telithromycin

Strong and moderate CYP3A4 inducers, including but not limited to avasimibe, phenytoin, rifampin, St John's wort, bosentan, efavirenz, etravirine, modafinil, and nafcillin

Antiepileptics

Investigational drugs^b

CYP=cytochrome P450

^a Topical ketoconazole is permitted.

^b Any active investigational drug in the context of a clinical study within the 3 months before baseline or plans to use such an investigational drug (other than the study treatment) during the study.

Benzodiazepines and non-benzodiazepine hypnotics are permitted to be used within specific restricted parameters during the study beginning from screening (Visit 1) until the end of the study treatment period (Day 57 or ET visit) as detailed in Table 3. Restrictions include maximum dosage allowed and the timing of use around assessments, ie, restricted medications should not be administered within 6 hours before any efficacy assessments (SHAPS, DARS, HAM-D17, Montgomery Åsberg Depression Rating Scale [MADRS], Clinical Global Impression – Severity [CGI-S],

Any usage of restricted

medications should be documented, including the date and the time of last dose taken, prior to the visits specified in the table. If the subject has taken any restricted concomitant medications within 6 hours of these scheduled assessments, then the site should reschedule these assessments to the next day (or within 2 to 3 calendar days).

Benzodiazepines must be at a stable dose equal to or less than the equivalent of 6 mg/day of lorazepam for 2 weeks before screening (Visit 1). As needed (prn) use of benzodiazepines is restricted; benzodiazepines should not be administered 6 hours prior to the subject's clinic visit (Table 3).

Table 3: Restricted Concomitant Medications

Medication Class	Dosage Allowed	Timing Restrictions
Benzodiazepines	Maximum of 6 mg/day of lorazepam or equivalent dose of another benzodiazepine for chronic use	Not permitted within 6 hours before any efficacy assessments (SHAPS, DARS, HAM-D17, MADRS, CGI-S, and [if applicable] performed on any study visit they are administered; refer to the schedule of assessments (see Table 8).
	Maximum of 2 mg/day of lorazepam or equivalent dose of another benzodiazepine for episodic use; up to 3 days per week	
Non-Benzodiazepine Hypnotics	Zolpidem up to 10 mg/day; zaleplon up to 20 mg/day; eszopiclone up to 3 mg/day; zopiclone 7.5 mg/day; or doxepin up to 6 mg/day for sleep	
Narcotic Analgesics	Only episodic use is allowed with Sponsor and/or Study Medical Monitor approval.	

; CGI-S=Clinical Global Impression – Severity;

DARS=Dimensional Anhedonia Rating Scale; HAM-D17=Hamilton Depression Rating Scale-17 Item;

MADRS=Montgomery Åsberg Depression Rating Scale;

SHAPS=Snaith-Hamilton Pleasure Scale;

7.2. Dietary and Other Restrictions

Grapefruit juice, grapefruit products, Seville oranges, and Seville orange products are prohibited from 7 days before Day 1 until the end of the study.

Any positive UDSs for disallowed substances (as specified in exclusion criterion #3) during conduct of the study must be discussed with the Sponsor or designee to determine the subject's disposition.

On the day of study visits, subjects may not use marijuana or alcohol until all assessments have been completed If a subject appears intoxicated at a study visit, efficacy assessments should not be performed that day and the site should reschedule these assessments to the next day (or within the window defined in the Schedule of Assessments (Table 8).

Subjects receiving psychotherapy (including CBT or BA) can continue receiving psychotherapy; however, CBT or BA must have been ongoing for the last 3 months prior to the start of the screening. With the exception of new CBT or BA, which is prohibited, no new psychotherapy is allowed during this study. Furthermore, the use of TMS and/or ECT is also prohibited during this study. Any change in existing therapy or new therapy must be documented on the concomitant therapies form.

8. DISCONTINUATION OF STUDY TREATMENT AND SUBJECT WITHDRAWAL

At any time during the study subjects can discontinue study treatment or withdraw their consent to participate in the study. The investigator must discontinue study treatment or withdraw any subject from the study at their request.

8.1. Discontinuation of Study Treatment

If a subject prematurely discontinues study treatment, the investigator will record the reason for discontinuation on the relevant eCRF. Data for any outcome measures, particularly the primary and secondary endpoints, as well as safety follow-up, are important to collect. Subjects will not be automatically withdrawn from the study and should continue participation in the study, regardless of study treatment compliance, unless consent for study participation has been withdrawn. For any subsequent study visits after study treatment is prematurely discontinued, subjects should have 1 final PK sample collected (ie, subsequent PK samples are not required); however, subjects should continue with study assessments at the study site or with virtual visits.

If medically indicated, treatment with medication listed under Section 7.1 is no longer prohibited after study treatment discontinuation.

Reasons for discontinuation from study treatment include but are not limited to:

- Withdrawal by subject
- Death
- Lost to follow-up

- Site termination by the Sponsor
- Study termination by the Sponsor
- AE
- Pregnancy
- Lack of efficacy
- Protocol deviation
- Investigator decision
- Sponsor decision

The investigator must discontinue study treatment if the subject experiences any of the following:

- If the type, frequency, or severity of any AE becomes unacceptable/intolerable
- If the subject is unable to tolerate the lowest allowable dose (80 mg or placebo)
- QTcF of >500 msec (cardiologist verified) on any ECG tracing
- If the subject is confirmed to be pregnant
- Withdrawal of consent for study treatment administration by subject
- If the subject exhibits suicidal behavior, or suicidal ideation of type 4 (active suicidal ideation with some intent to act, without specific plan) or type 5 (active suicidal ideation with specific plan and intent) based on the C-SSRS or according to the investigator's clinical judgement
- Study treatment should be discontinued with appropriate clinical follow-up (including repeat laboratory tests) until a subject's laboratory profile has returned to normal/baseline status), if any of the following occur (see Appendix D for additional detail):
 - ALT or AST $>8 \times ULN$, or
 - ALT or AST >5×ULN and persists for more than 2 weeks, or
 - ALT or AST >3×ULN in conjunction with elevated total bilirubin >2×ULN or INR >1.5
 - ALT or AST >3×ULN with appearance of fatigue, nausea, vomiting, right upper quadrant pain or tenderness, fever, rash and/or eosinophilia (>5%)
 - ALP elevations >1.5×ULN in conjunction with elevated TBLI >1.5×ULN, or
 - 5'nucleotidase >2×ULN, or GGT >5×ULN, or AST/ALT >3×ULN.

Every effort should be taken to obtain follow-up data for any subject who discontinues study treatment because of an AE, abnormal laboratory test, vital sign measurement, physical examination, or ECG finding.

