APPENDIX D. LIVER FUNCTION TEST MONITORING

If a subject is noted to have ALT or AST elevated >3×ULN, the investigator will take the following actions:

- Obtain follow-up laboratory tests: ALT, AST, ALP, GGT, and total bilirubin, direct bilirubin, PT, and INR within 48 to 72 hours after the abnormality was noted.
- Assess whether the subject has experienced any clinical manifestations such as fatigue, low-grade fever, anorexia, nausea/vomiting, right upper quadrant pain, jaundice, or pruritus.
- Inform the Study Medical Monitor.

If symptoms persist or repeat testing shows ALT or AST >3×ULN, repeat ALT, AST, ALP, GGT, total bilirubin, direct bilirubin, and INR two or three times weekly. The frequency of retesting can decrease to once a week or less if abnormalities stabilize or the study treatment has been discontinued and the subject is asymptomatic. Serial testing should continue until the liver function tests return to baseline values. Further assessment will be conducted as clinically indicated, in consultation with the Study Medical Monitor. The study treatment may be discontinued by the investigator in consultation with the Study Medical Monitor, or at the request of the Study Medical Monitor

The Study Medical Monitor should also be promptly notified if any of the following criteria are met:

- ALP >1.5×ULN in conjunction with elevated TBILI >1.5×ULN, or
- 5'nucleotidase >1.5×ULN, or GGT >2×ULN, or AST/ALT:>1.5×ULN
- ALP >2×ULN persisting for longer than 3 days;
- ALP $>3 \times ULN$;
- Total bilirubin >2.0×ULN;
- Creatinine >2 mg/dL;
- Baseline elevations in liver enzymes <3×ULN, yet worsen by 2-fold increases above Baseline values after study drug exposure.

Additionally, the study treatment should be discontinued immediately if any of the following criteria has been meet:

- ALT or AST >8×ULN, or
- ALT or AST >5×ULN and persists for more than 2 weeks, or
- ALT or AST >3×ULN in conjunction with elevated total bilirubin >2×ULN or INR >1.5.
- ALT or AST >3×ULN with appearance of fatigue, nausea, vomiting, right upper quadrant pain or tenderness, fever, rash and/or eosinophilia (>5%)
- ALP elevations >1.5×ULN in conjunction with elevated TBLI >1.5×ULN or
- 5'nucleotidase >2×ULN or GGT >5×ULN or AST/ALT >3×ULN

Signature Page for VV-CLIN-002587 v1.0

Approval Task	
	Clinical
	25-Mar-2023 05:55:50 GMT+0000

Signature Page for VV-CLIN-002587 v1.0

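### The liver stopping lists in Protocol Section 8.1 and Appendix D end with an unqualified AST/ALT >3×ULN item, which conflicts with the graded criteria beside it and with Appendix D's discretionary pathway for the same trigger

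*Protocol*

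**What the plan says.** Section 8.1 of the protocol opens its list with "The investigator must discontinue study treatment if the subject experiences any of the following". The liver sub-list sits under that sentence and is itself triggered by any one of its items. Its ALT/AST content is:

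- four graded criteria: above 8×ULN; "ALT or AST >5×ULN and persists for more than 2 weeks"; above 3×ULN with total bilirubin >2×ULN or INR >1.5; above 3×ULN with listed symptoms, rash or eosinophilia;
- after a separate ALP/bilirubin bullet, a last bullet that names 5'-nucleotidase and then "GGT >5×ULN, or AST/ALT >3×ULN".

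Section 8.1 sends the reader to Appendix D for more detail. Appendix D has three relevant parts:

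- **A pathway for ALT or AST >3×ULN.** Retest within 48 to 72 hours, check for clinical manifestations and inform the Study Medical Monitor. Then "If symptoms persist or repeat testing shows ALT or AST >3×ULN, repeat ALT" and the rest of the panel two or three times weekly. The same paragraph adds: "The study treatment may be discontinued by the investigator in consultation with the Study Medical Monitor".
- **A notification list.** It includes an ALP/bilirubin bullet followed by a bullet with 5'-nucleotidase >1.5×ULN, GGT >2×ULN or AST/ALT >1.5×ULN.
- **An immediate-stop list**, introduced as additional to the above. It repeats the Section 8.1 liver items, including the closing "GGT >5×ULN or AST/ALT >3×ULN".

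**The concern.** A list in which any one item suffices is governed by its broadest item. An unqualified 3×ULN item makes the narrower items that start at 3×, 5× or 8×ULN pointless, which suggests that the printed text is not what its authors meant. The same threshold also opens a pathway in which stopping is optional, so the protocol attaches two different levels of obligation to one laboratory value.

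Hepatobiliary injury is the nonclinical risk that Section 2.2 singles out for monitoring. With about 20 centers planned, an investigator facing an isolated transaminase rise needs one instruction. Two answers to the same question invite inconsistent handling and avoidable protocol deviations.

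**Working it through.** The plan states no figure on this point, so the check is logical.

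**Step 1: containment.** Let m be the larger of ALT and AST in multiples of ULN, and read AST/ALT as either enzyme. The bare item is m > 3. The graded items are m > 8; m > 5 and persisting; m > 3 and (bilirubin or INR raised); m > 3 and symptoms. Each implies m > 3, so none can be met unless the bare item is met.

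**Step 2: enumeration.** ALT and AST were each set to 1, 2, 3, 3.5, 5.5 and 8.5×ULN and crossed with bilirubin >2×ULN, INR >1.5 and symptoms (yes/no each). Persistence beyond 2 weeks was allowed only where m > 5.

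- States without persistence: 36 enzyme pairs × 8 = 288.
- States with persistence: (36 − 16) pairs × 8 = 160.
- Total: 288 + 160 = 448.
- Bare item met: (36 − 9) × 8 + 160 = 376.
- Bare item met and no graded item met: pairs whose larger value is 3.5 or 5.5, 25 − 9 = 16, in one state each = 16.
- Both met: 376 − 16 = 360.
- Graded item met without the bare item: 0.

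These are counts of logical states, not of expected subjects.

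**Step 3: what each passage requires.** The 5'-nucleotidase, GGT and ALP/bilirubin items are taken as not met.

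| ALT or AST pattern | Graded items | Bare item | Appendix D >3×ULN pathway |
|---|---|---|---|
| >3 to 8×ULN, not >5×ULN for more than 2 weeks, no qualifying bilirubin, INR or symptom | no stop | stop | retest; stopping optional |
| >3×ULN with bilirubin >2×ULN or INR >1.5 | stop | stop | retest; stopping optional |
| >3×ULN with listed symptoms | stop | stop | retest; stopping optional |
| >5×ULN for more than 2 weeks | stop | stop | retest; stopping optional |
| >8×ULN | stop | stop | retest; stopping optional |

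In the last four rows the graded items can be read as exceptions to a discretionary pathway, which is coherent. In the first row the bare item is the only source of a mandatory stop. It removes the discretion that the pathway grants at that threshold.

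**Step 4: dependence on the reading of AST/ALT.** If the bare item required both enzymes above 3×ULN, full redundancy would fail. The >8×ULN criterion is met in (36 − 25) × 16 = 176 states. In 2 × 3 × 16 = 96 of them the other enzyme is at or below 3×ULN, so the bare item is not met.

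**The case against.** The best counter-argument is that the last two bullets are really one compound rule: ALP above 1.5×ULN together with raised bilirubin, or 5'-nucleotidase, or GGT, or AST/ALT. The notification list has the same two-bullet construction. Read as standing alone there, AST/ALT >1.5×ULN would make the separate instruction to inform the Study Medical Monitor at >3×ULN largely redundant too. On the compound reading the graded criteria keep their effect and the conflict largely disappears. A second argument is that only this type of bullet is written AST/ALT, while every graded item says ALT or AST, so both enzymes might be meant.

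Both readings are possible, but neither is stated. A trailing *or* does not show that two bullets belong together, because "ALT or AST >8×ULN, or" also ends with one and plainly joins separate items. If either reading was intended, the text misstates it in Section 8.1 and again in Appendix D, and it still needs correcting.

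Some stronger conclusions are tempting and should not be drawn:

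- **That Appendix D tells sites to keep such subjects on treatment.** It does not say so. Its retest paragraph also covers subjects already off drug, and Section 8.1 pairs stopping with repeat laboratory tests. Retesting and stopping are compatible.
- **That two sites could act in opposite ways and both comply.** On the printed text, a site that continued drug above 3×ULN would breach both stop lists. The discretionary sentence is not wholly empty either, since its paragraph also applies when symptoms persist, possibly after the enzymes have fallen.
- **That the affected range ends at 5×ULN.** It reaches 8×ULN when a value above 5×ULN has not persisted for more than 2 weeks.
- **That the primary analysis is materially affected.** Subjects who stop treatment remain in follow-up through Day 57 (Protocol Sections 4.1 and 8.1) and are analyzed under a treatment policy strategy (SAP Section 7.3.2). A stop is therefore not in itself missing data, and no effect has been quantified.

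Few subjects may be involved. Exclusion criterion 11 removes AST or ALT >2×ULN at screening, and Section 2.2 reports no clinically meaningful liver results in the clinical studies it names.

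**Conclusion.** The inconsistency is real and in the current text. It lies in two places: between the optional wording of the Appendix D pathway and the mandatory or immediate wording of the stop lists, and between the bare item and the graded items beside it. It also exists within Appendix D alone, so editing Section 8.1 by itself would not remove it.

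As printed, with AST/ALT meaning either enzyme, four of four graded ALT/AST criteria have no separate effect. The contradictory instructions meet in the pattern shown in the first row of the table. That conclusion rests on the last bullet standing alone; under the compound or both-enzymes reading, the fault becomes a misprint or an undefined term.

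This is an error of wording in a safety stopping rule. Redundancy does not by itself leave a gap in protection, because read literally the broadest stop governs. A mandatory safety rule should nevertheless not need interpretation, so it should be corrected. The number of subjects affected cannot be estimated from the documents.

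**What to change.** Reconcile four pieces of text together: the Section 8.1 liver list, the Appendix D >3×ULN pathway, the Appendix D immediate-stop list and the similarly built Appendix D notification list. Each laboratory pattern should lead to one action with one level of obligation. State explicitly whether the last bullet stands alone or belongs to the ALP/bilirubin rule, and whether AST/ALT means either enzyme or both. Which rule stands is for the clinical team to decide; this review takes no view on the threshold.

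The cost is a protocol wording change in two places (Section 8.1 and Appendix D) and a clarification letter to sites. No change to the analysis plan follows from this point.

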8.2. Withdrawal from Study

If a subject prematurely withdraws from the study, the investigator will record the reason for withdrawal on the relevant eCRF. All subjects who withdraw from the study prematurely will be asked to have all ET assessments performed and, unless consent has been withdrawn, will be asked to come back for 2 safety follow-up visits at 4 and 8 weeks after last dose of study treatment. If a subject's last dose of study treatment was >8 weeks before the ET visit, the Safety Follow-Up visits are not needed. If a subject's last dose of study treatment was >3 weeks but <8 weeks before the ET visit, only the Week 16 Safety Follow-Up visit is needed (ie, only one Safety Follow-Up visit approximately 8 weeks after the last dose of study treatment is needed).

Reasons for withdrawal from study include, but are not limited to:

- Withdrawal by the subject
- AE
- Death
- Lost to follow-up
- Site terminated by Sponsor
- Study terminated by Sponsor
- Protocol deviation
- Investigator decision
- Sponsor decision

8.3. Sponsor's Termination or Temporary Halt of Study or Study Site

The Sponsor or designee reserves the right to close a study site, terminate, or temporarily halt the entire study, or terminate or temporarily halt the study at individual sites, at any time for any reason. If the study is prematurely terminated or temporarily halted, the Sponsor shall promptly inform the investigators, the Institutional Review Boards (IRBs)/Independent Ethics Committees (IECs), the regulatory authorities, and any contract research organizations (CROs) used in the study of the reason for termination or temporary halt, as specified by the applicable regulatory requirements. The investigator shall promptly inform the subject and should assure appropriate therapy and/or follow-up.

9. STUDY ASSESSMENTS AND PROCEDURES

A schedule of assessments is provided in Table 8 (Appendix A). No study procedures should be performed until after the subject has signed the informed consent form (ICF). Subject-related events and activities including specific instructions, procedures, concomitant medications, dispensing of study treatment, and descriptions of AEs should be recorded in the appropriate source documents and eCRFs.

When the following assessments are scheduled to be performed at the same timepoint, the order of priority will be as follows: vital signs, physical and neurological examination, questionnaires, ECG, and blood sampling for safety and PK.

9.1. Screening Assessments and Procedures

9.1.1. Subject Registry Database Review Consent

Clinical study subject registries seek to reduce subjects from enrolling into multiple clinical studies by identifying potential duplicates before enrollment. This study will utilize 1 or more subject registry database(s) at sites where they are available. At the time of providing informed consent for the study, the investigator or designee will explain the subject registry database review process to the subject and witness the signature.

During screening, site staff who have received training and login information to access the registry will enter the subject identification number and authorized subject identifiers on the registry website. An immediate report based on matches to exclusion criterion #17 in Section 5.2 will be generated and should be printed for source documentation. The report will specify either (1) no matches found, (2) a potential match was found to 1 or more specified criteria, and/or (3) the subject matches 1 or more specified criteria. The registry database check should be performed as early as possible at the screening visit to avoid unnecessary procedures.

9.1.2. Mini-International Neuropsychiatric Interview

The MINI is a structured diagnostic interview that was originally developed for DSM-IV and ICD-10 disorders, for multicenter clinical studies and epidemiology studies (Lecrubier et al., 1997; Sheehan et al., 1998). The MINI has been validated against the Structured Clinical Interview for DSM Patients and Composite International Diagnostic Interview for ICD-10. The MINI has been translated and validated in over 70 languages and has been updated to match DSM-5 (MINI 7.0.2).

The MINI may be administered by a healthcare professional with a clinically relevant qualification (eg, psychiatrist, psychiatric nurse or psychologist) and documented experience assessing patients with MDD. Raters must be trained and certified for administration of MINI in this study.

Specific timepoints for collection are provided in Table 8.

